6.7.3. Procedures at Unscheduled Visits

At any time during the study, the patient may make unscheduled visits to the investigational centre, as required by his/her clinical status. The following procedures may be performed, at the Investigator's discretion:

- Physical and neurological examinations;
- Collection of signs and symptoms of HAT, if any, since the previous visit;
- Investigation of any concomitant condition that could have prompted the visit;
- Collection of blood and/or lymph samples for testing for parasites, if indicated;
- Collection of CSF, only if symptoms suggesting a relapse of HAT are present;
- Additional safety assessments such as ECG, haematology, biochemistry or urine analysis.
- Collection of AEs, in accordance with Section 6.8.4.
- For patients treated on an out-patient basis, blood sampling for PK analysis in the event of an unscheduled visit between Day 1 and Day 11.

Confidential Page 39 of 83

6.8. Safety Assessments

6.8.1. Definitions

Adverse Event

An adverse event (AE) is any untoward medical occurrence in a patient or clinical trial subject administered a medicinal product and which does not necessarily have a causal relationship with this treatment.

An AE can therefore be any unfavourable and unintended sign (including an abnormal laboratory test or ECG finding, for example), symptom or disease temporally associated with the use of a medicinal product, whether or not considered related to the medicinal product.

The definition of an AE includes worsening of any pre-existing conditions or any abnormality on a test procedure (e.g. ECG) or laboratory test (haematology, biochemistry) that occurs or worsens (in severity or frequency) after starting the IMP and that the Investigator considers to be clinically significant, unless it is associated with a previously reported clinical event.

Of note, lack of efficacy is not an AE.

Laboratory test abnormalities may be considered to be "clinically significant", and should therefore be reported as AEs, if they fulfil any of the following criteria:

- The abnormality suggests a disease and/or organ toxicity and the abnormality was not present at baseline or is considered to have worsened abnormally from baseline,
- The abnormality leads to discontinuation of the IMP,
- The abnormality requires a medical intervention or treatment.

Serious Adverse Event

A serious adverse event (SAE) is any event that:

- results in death;
 - o i.e. causes or contributes to death;
- is life-threatening;
 - i.e. in this context refers to a reaction in which the patient was at risk of death at the time of the reaction; it does not refer to a reaction that hypothetically might have caused death if it had been more severe;
- requires hospitalisation or prolongation of existing hospitalisation;
 - i.e. the AE required hospitalisation for at least 24 hours or prolonged hospitalisation beyond the duration initially expected. Hospitalisation for surgery planned prior to study entry, for social reasons, for elective surgery

Confidential Page 40 of 83

(e.g. cosmetic surgery) or in the context of usual management of the disease (including treatment adjustment) will not be considered as an SAE. Similarly, hospitalisation of patients initially treated on an out-patient basis will not be considered as an SAE solely based on the criterion of hospitalisation because, in accordance with Section 6.5, they are to remain in hospital, as are patients initially hospitalised, up to Day 13 or 18. The other seriousness criteria remain valid. This includes hospitalisation for reasons related to non-compliance with treatment, including for a non-serious AE based on the other seriousness criteria;

- results in persistent or significant disability or incapacity;
 - i.e. an AE that leads to significant impairment of the patient's ability to carry out normal activities;
- is a congenital anomaly or birth defect in the child or foetus of a female patient exposed to treatment prior to conception or during pregnancy;
- is an important medical event, i.e. an event that may not be immediately lifethreatening or result in death, but that jeopardises the patient's safety or requires an intervention to prevent one of the outcomes above.

In the study, ALT or AST levels above 3 ULN associated with total bilirubin above 2 ULN will be considered to be SAEs.

Any suspected transmission of an infectious agent via the IMP will also be considered as an SAE.

Any other event defined as serious in the protocol will be reported as an AE and as an SAE in accordance with the procedure described in Section 6.8.5.

For the purposes of the study, hospitalisation for non-complicated delivery will not be considered as an SAE.

6.8.2. Collection of Information on AEs

AEs may be observed directly by the medical personnel or spontaneously reported by the patient or his/her caregiver. For patients treated in hospital, potential AEs will be collected by the medical personnel each day during the treatment period and up to the EoH visit. The Investigator or qualified study personnel should examine any patient who experiences an AE as soon as possible. All medical measures necessary to ensure the patient's safety and well-being must be implemented. For patients treated on an out-patient basis, potential AEs that occur during the treatment period will be collected at the EoT visit, i.e. Day 11, or at any unscheduled visit to the centre between Day 1 and Day 11.

After the end of the periods mentioned above, AEs will be collected as described in Section 6.8.4.

Confidential Page 41 of 83

Information on AEs will be recorded in the corresponding section of the CRF using concise medical terms and avoiding vague, ambiguous or colloquial language. When a clinically significant laboratory abnormality is reported, whenever possible, a clinical diagnosis should be reported as the AE rather than simply an abnormal value, e.g. "anaemia" instead of "reduced red blood cell count".

6.8.3. Follow-up on AEs

Any AE must be followed up until it resolves, until the Investigator considers it to be "stable" or "chronic", or until the end of the patient's participation in the study, i.e. until the end-of-study page of the CRF for the patient has been completed.

If the AE is a clinically significant laboratory test abnormality, a repeat test is to be performed 2 to 4 days later and then at regular intervals until the value returns to normal or to the baseline level.

6.8.4. AE Collection Period

The collection period for AEs that occur in the context of the study is defined as follows:

- For any AE that is not considered to be an SAE: from the first intake of fexinidazole on Day 1 until the EoH visit (Day 13-18) for patients treated in hospital. For patients treated on an out-patient basis, the observation period extends to the EoT visit (Day 11).
- For **any SAE**: from the time of enrolment of the patient in the study (i.e. after signing the informed consent) and **until the end of follow-up** (18 months).

AEs that occur during the Screening period (after signing the informed consent) prior to the start of treatment and that are considered to be related (i.e. a reasonable possibility) to participation in the study, will also be collected by the medical personnel and recorded in the CRF.

In addition, any non-serious AE that occurs after the collection period and that the Investigator considers to be related (i.e. a reasonable possibility) to the IMP, must also be collected.

6.8.5. Reporting Requirement for AEs

Information on AEs must be assessed by a physician. The Investigator must determine whether the AE is considered to be serious or not, if necessary with the assistance of the Coordinating Investigator and the study monitor. This classification will determine the reporting procedure for the event.

All SAEs must be reported to the study monitor **immediately, and at the latest 24 hours** after the Investigator becomes aware of the event. The information must be reported, initially, by telephone and/or Short Messaging Service (SMS), and then using the SAE reporting form, which is to be sent by e-mail. The report must

Confidential Page 42 of 83

include the nature of the SAE (if possible a clinical diagnosis), the date and nature of onset, duration, severity, relationship to IMP (assessed with the assistance of the Coordinating Investigator, as needed; reasonable possibility see Section 6.8.7.), measures taken and outcome, as well as any other relevant clinical or laboratory data.

Additional information must be sent as soon as it becomes available, using the SAE follow-up reporting form. All follow-up reports must be sent as quickly as possible and, if possible, within 5 working days after the new information becomes available. A close-out follow-up report must be sent after the final assessment of the case, specifying the outcome of the SAE as "recovery", "recovery with sequelae", "death" etc.

SAEs must be reported using the AE reporting form in the CRF and the SAE reporting form. It should be noted that the SAE reporting form is not the same as the form in the AE section of the CRF. The two forms must be completed in a consistent manner, using the same medical terminology.

All AEs must be recorded in the CRF.

For the purposes of this study, the Coordinating Investigator will be responsible for reporting suspected unexpected serious adverse reactions (SUSARs), considered to be related to the IMP (reasonable possibility), as well as all SAEs, to the Ethics Committee of the country and to other appropriate governing bodies in accordance with national regulatory requirements.

The Sponsor will be responsible for reporting SUSARs and SAEs to the regulatory authorities in accordance with current regulations. The Investigator Brochure will be used as the reference safety information on the IMP, and the expectedness of Aes will be assessed by the Sponsor using this information.

6.8.6. Grading of AE Severity

The severity of the AE will be graded according to NCI CTCAE, version 4.03 (14) and, for certain laboratory parameters, modified CTCAE (see Appendix 6- CTCAE v4.03 adapted, p 81). If the AE is not described in the CTCAE, version 4.03, the Investigator will use the terms "mild", "moderate" or "severe" to describe the maximum severity, as defined below:

Mild The patient is conscious of the event or symptom, which is easily tolerated; the event does not lead to any reduction in the patient's activities of daily life.

Moderate The patient feels discomfort such that it reduces or interferes with the patient's activities of daily life.

Severe Significant functional impairment: the patient is unable to carry out activities of daily life and/or the event is life threatening.

Confidential Page 43 of 83

Information on the severity of the AE must be recorded in the Adverse Events section of the CRF.

It is important to distinguish between the severity and the seriousness of an AE: a severe AE is not necessarily a serious AE, since the criteria for seriousness (see Section 6.8.1 Definitions, Serious Adverse Event; p 40) are different from the criteria for severity.

6.8.7. Assessment of AE Causality

For each AE, the Investigator must assess the possible causal relationship between the IMP and the AE, with the assistance of the Coordinating Investigator, in order to determine whether there is a reasonable possibility that the IMP caused or contributed to the AE.

The causal relationship between the IMP and the AE is assessed by the Investigator after a detailed analysis of the event in terms of the biological plausibility, taking into account possible unrelated causes, pre-existing medical conditions, concomitant medication, the temporal relationship between intake of the IMP and onset or worsening of the AE, and the known patterns of response to fexinidazole in general.

The two types of causal relationships are defined as follows:

- Not related: there is no reasonable possibility of a causal relationship.
- Related: there is at least a reasonable possibility of a causal relationship between the IMP and the AE. This means that there are facts (evidence) or features that suggest a causal relationship.

6.8.8. Exposure in utero

Four pregnancy tests are planned during the study: at Screening (Day -1), at the EoT visit (Day 11), and at the 3-month and 6-month follow-up visits. Pregnancy is not a non-inclusion criterion. Women in the second or third trimester of pregnancy will be allowed to participate in the study, however they will be treated in hospital. First-trimester pregnancy is considered to be a temporary non-inclusion criterion (see Section 4.2 Non-inclusion Criteria; p 26).

Pregnancy is not considered to be an AE, regardless of when it is detected.

Nevertheless, the Investigator must report any pregnancy that occurs during the treatment period or that is detected at the 3-month or 6-month follow-up visits, using the appropriate Pregnancy Reporting Form. The pregnancy must be reported whether or not an AE occurred. If known, the due date should be specified.

The Investigator must monitor the patient until the term of the pregnancy, i.e. full term or preterm, in the event of a miscarriage. The Investigator must provide

Confidential Page 44 of 83

information on the outcome of the pregnancy using the pregnancy follow-up reporting form.

A physician, preferably a paediatrician, should examine the infant at birth and submit a report using a Newborn Follow-up Form. The child's age must be collected and recorded on the form. The child will undergo diagnostic testing, in accordance with PNLTHA procedures, in order to rule out vertical transmission of the parasite. If the child is found to be HAT-positive, s/he will be managed by the PNLTHA.

The Investigator will offer the patient follow-up on infants exposed to the IMP *in utero* until they reach 24 months of age. As far as possible, stillborn infants should be examined by a physician to ascertain the cause of death.

Any SAE that occurs in a pregnant patient (exposed to the IMP or who is found to be pregnant any time up to the 18-month visit) or that concerns the pregnancy or the foetus, will be reported using the SAE reporting form in the same manner as any other SAE. Any non-serious AE concerning a pregnant patient that occurs during the AE reporting period will be collected using the AE form in the CRF (see Section 6.8.4. AE Collection Period, p 42).

6.8.9. Exposure During Breastfeeding

The Investigator will offer the patient follow-up on infants exposed to the IMP via breastfeeding, until they reach 24 months of age. Follow-up will be recorded using the Newborn Follow-up Form, where the child's age must be recorded.

The child will undergo diagnostic testing, in accordance with routine practice, in order to rule out transmission of the parasite via the mother's milk.

If the child is found to be HAT-positive, s/he will be managed by the PNLTHA.

7. Study Duration

Based on an enrolment period of approximately 36 months and a follow-up period of 18 months, the duration of the study will be 54 months.

Each patient's participation in the study will last approximately 19 months and will include:

- a Screening period (including treatment of concomitant disease) of up to 15 days;
- a treatment period of 10 days;
- an in-hospital follow-up period of 3 to 8 days;
- an out-patient follow-up period of 18 months.

Confidential Page 45 of 83

8. Withdrawal Criteria

8.1. Temporary Interruption of Treatment

Patients treated on an out-patient basis must not under any circumstances discontinue treatment, even temporarily. However, if temporary interruption of treatment seems inevitable, the patient must contact the Investigator or come to the investigational centre before interrupting treatment. The Investigator will decide on the appropriate course of action and will inform the Sponsor as quickly as possible.

Temporary interruption of treatment will not necessarily lead to patient withdrawal from the study. In some cases, treatment may be interrupted for a maximum of one day, i.e. one missed dose of fexinidazole, and treatment will therefore be delayed. Treatment may be reintroduced at the discretion of the Investigator. One additional day of treatment will be added to make up for the missed dose, and the EoT visit will take place on Day 12. The patient should continue the visits and study procedures as planned, taking into account the delay. The reasons for interrupting treatment must be recorded in the CRF.

8.2. Definitive Discontinuation of Treatment

The Investigator, in agreement with the Principal Investigator, will discontinue the study treatment in the following cases:

- Severe skin reaction;
- ALT or AST > 8 ULN;
- ALT or AST > 3 ULN in association with total bilirubin > 2 ULN;
- ALT or AST > 3 ULN in association with fatigue, nausea, vomiting, abdominal pain or tenderness in the right upper quadrant, fever, rash and/or eosinophilia (> 5%);
- Any condition that requires treatment discontinuation for medical reasons, as decided by the Investigator.

If a patient is withdrawn from the study before the end of treatment, the physician will make all necessary arrangements to ensure that s/he receives the appropriate treatment for the condition in question.

8.3. Patient Withdrawal from the Study and Replacement of Patients

A patient may be withdrawn from the study in the following cases:

- Withdrawal of consent by the patient or his/her legal representative;
- Study termination by the Sponsor.

If the patient withdraws his/her consent, the Investigator must ensure the patients safety and well-being and take appropriate measures. When possible, the Investigator should perform an end-of-study examination.

Confidential Page 46 of 83

If a patient decides to withdraw from the study, the Investigator must ensure that withdrawal is not related to an AE. If a patient withdraws from the study due to an AE, all measures must be taken as needed to clearly document the outcome of the AE.

Data collected prior to withdrawal of the patient will be taken into account in the PK, efficacy and safety analyses.

Patients withdrawn from the study will not be replaced.

8.4. Patients Lost to Follow-up

If a patient does not attend a protocol-planned visit, all possible measures must be taken to contact him/her. In all cases, the Investigator must take all possible measures to document the course of the patient's condition.

9. Data Analysis and Statistical Methods

A first draft of the full Statistical Analysis Plan (SAP) will be prepared. It will provide a more detailed description of the statistical methods. The SAP will be reviewed and, if necessary, amended prior to final database lock. Successive versions will be dated and numbered.

9.1. Sample Size Determination

The sample size determination is based on the primary analysis. The expected success rate is between 87% and 91% depending on the percentage of early-stage patients included in the sample. The success rate for patients with late-stage HAT should be slightly below the expected success rate of 89% in the pivotal study, DNDIHATFEX004, which has a restricted, more homogeneous population.

As concerns early-stage patients, a meta-analysis performed by Hümbelin (11), on a sample of 2524 patients treated with pentamidine and indexed in the databases of four non-governmental organisations showed a relapse rate (presence of trypanosomes or CSF WBC \geq 20/µL) of 5.63% in patients followed for 6 months or less (142/2524), 8.20% in patients followed for 12 months or less (207/2524) and 9.23% in patients followed for 18 months or less. The expected success rate for early-stage patients should be close to 92%.

A sample size of 174 patients provides a precision of \pm 5% in the estimate if the expected success rate is 87% and if a Wald confidence interval is used.

Because the confidence interval will be calculated with an exact method (Clopper-Pearson approach) the lower arm of the 95% CI will be longer than the upper arm. The precision for the lower arm will be close to 6% and that of the upper arm will be close to 4.5 % if we consider an expected success rate of 87%. The precision will be greater if the success rate is higher.

Confidential Page 47 of 83

9.2. Definition of Study Populations included in the Analyses

Three patient populations will be used in the statistical analyses, as follows:

- The intent-to-treat (ITT) population, comprising all patients included in the study, regardless of whether or not they took the IMP;
- The modified intent-to-treat (mITT) population, comprising all patients who took at least one tablet of fexinidazole;
- The per protocol (PP) population, comprising all patients who completed the study in accordance with the protocol with no major violations that could interfere with the efficacy evaluation. Premature withdrawal from the study due to treatment inefficacy or intolerance will not be considered as a protocol violation.

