9.5.2. Sensitivity Analysis

The success rates at 12 and 18 months will be estimated along with the 95% exact confidence intervals on the per protocol population of patients.

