## 5. ANALYSIS SETS AND SUBGROUPS

The analysis sets are the following.

- **Screened HAT positive patients:** all HAT positive patients who signed the informed consent.
- **Intent-to-treat (ITT) population:** all patients included in the study, regardless of whether or not they took the IMP (but the treatment unit was provided to the outpatient);
- **Modified intent-to-treat (mITT) population:** all patients who took at least one tablet of fexinidazole;
- **Evaluable patients:** patients included in the mITT and excluding:
  - Patients lost to follow-up at 18 months (for primary efficacy endpoint and secondary efficacy outcome at 18 month), patients lost to follow-up at 12 months (for secondary efficacy outcome at 12 month), except those who were a failure before being lost to follow-up.
  - Patients with no post-treatment lumbar puncture
  - Patients who died for reasons clearly unrelated to efficacy or safety or disease evolution (\*\*).
- **Per protocol (PP):** all patients who completed the study in accordance with the protocol with no major violations (cf. [Section 8.2](#)) that could interfere with the efficacy evaluation. An out-patient who did not take any tablet of the IMP or with a compliance below 75% of the expected number of tablets is not per protocol unless it is due to lack of tolerance. Premature withdrawal from the study due to treatment inefficacy or intolerance will not be considered as a protocol violation.

Two study cohorts are defined:

- **Inpatients:** patients treated in hospital,
- **Outpatients:** patients treated on an outpatient basis. Note that outpatients that would require hospitalization (for any reason) will be analyzed according to their initial cohort (i.e. as “outpatients”).

The following subgroups are defined according to the stage and severity of disease at inclusion:

- Stage 1
- Intermediate stage
- Stage 1 + Intermediate stage
- Stage 2
- WBC in CSF  $\leq$  100 /  $\mu$ L
- 100 < WBC in CSF  $\leq$  400 /  $\mu$ L
- WBC in CSF  $>$  400 /  $\mu$ L

For the analysis, these subgroups will be calculated as described in Table 1. Subgroups analyses are specified in [Section 8](#).

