### Sensitivity analysis

A descriptive analysis of the primary efficacy endpoint with the 95% exact Clopper-Pearson confidence intervals will be provided on the Evaluable patients set and PP set (overall).

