## 8.7. Analysis of the secondary endpoints

### 8.7.1. Analysis of the endpoint at 12 months

The endpoint at 12 months will be analysed as described for the primary endpoint (see above [Section 8.6](#): “primary”, “sensitivity” and “secondary” analyses).

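### One per-protocol set, defined by completing the 18-month study, also serves the 12-month success rate, so membership of the 12-month analysis depends on events after month 12

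*Protocol*

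**What the plan says.** Protocol 9.2 gives one PP population, "comprising all patients who completed the study in accordance with the protocol with no major violations that could interfere with the efficacy evaluation", and adds: "Premature withdrawal from the study due to treatment inefficacy or intolerance will not be considered as a protocol violation". SAP 5 keeps the same core, "all patients who completed the study in accordance with the protocol with no major violations", and adds a 75% tablet-compliance rule for out-patients. Neither document has a 12-month version of PP.

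Protocol 7 puts a patient's participation at about 19 months, including 18 months of out-patient follow-up, so finishing the study means reaching month 18. The disposition template in SAP 9.2.1 fits this: death, loss to follow-up and consent withdrawal are listed under premature withdrawal, apart from study completion.

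The set is used at both time points. Protocol 9.5.2 says "The success rates at 12 and 18 months will be estimated along with the 95% exact confidence intervals on the per protocol population". SAP 8.6 states that the sensitivity results "will be provided on the Evaluable patients set and PP set (overall"), and SAP 8.7.1 carries this over: "The endpoint at 12 months will be analysed as described for the primary endpoint".

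In the same SAP section, the Evaluable set does follow the time point. It excludes losses at 18 months for the 18-month outcome and, separately, "patients lost to follow-up at 12 months (for secondary efficacy outcome at 12 month"), and it keeps patients who had failed before being lost.

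Two other places describe PP differently. Protocol 9.3 (disposition) and SAP 8.2 (protocol deviations) refer only to the absence of major violations and do not mention completion.

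**The concern.** An analysis at month 12 should not select patients by what happens between months 12 and 18. Under the definition as written, someone whose month-12 lumbar puncture showed a success, and who is then lost, withdraws consent or dies of an unrelated cause, is not a completer and drops out of the 12-month PP rate. A patient withdrawn for relapse by month 12 is covered by the inefficacy exemption and stays. Among patients with an observed month-12 outcome, later attrition therefore tends to remove successes.

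At stake is what the 12-month PP rate can be used for. As a sensitivity analysis it is meant to show whether the 12-month result holds in patients who followed the protocol. If part of any gap between it and another 12-month rate comes from attrition after month 12, it does not answer that question cleanly. It also discards patients whose 12-month outcome is known.

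**Working it through.** **The plan's own figure.** Inputs from protocol 9.1: expected success 87%, precision 5 points, Wald 95% interval. n = 1.96² × 0.87 × 0.13 / 0.05² = 173.8, which rounds up to 174. The exact interval at 151/174 has arms of 5.95 points (lower) and 4.65 points (upper), in line with the stated values close to 6 and 4.5. The planning figures reproduce and are not in dispute.

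**Inputs for the check.** N = 174 and success of 87% to 91% (protocol 9.1), giving 151, 155 or 158 successes at 87%, 89% and 91%. The share of 12-month successes lost between months 12 and 18 is not in the documents; 5%, 10% and 15% are assumed. As a simplification, all 174 patients would be in a PP set anchored at month 12, and every 12-month failure stays.

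**Formula.** With s successes, f failures and k successes lost after month 12, the rate moves from s/(s + f) to (s − k)/(s − k + f).

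| Anchored at month 12 | Share lost (k) | With 18-month completion required | Change (points) |
|---|---|---|---|
| 151/174 = 86.8% | 5% (8) | 143/166 = 86.1% | −0.64 |
| 151/174 = 86.8% | 10% (15) | 136/159 = 85.5% | −1.25 |
| 151/174 = 86.8% | 15% (23) | 128/151 = 84.8% | −2.01 |
| 155/174 = 89.1% | 5% (8) | 147/166 = 88.6% | −0.53 |
| 155/174 = 89.1% | 10% (16) | 139/158 = 88.0% | −1.11 |
| 155/174 = 89.1% | 15% (23) | 132/151 = 87.4% | −1.66 |
| 158/174 = 90.8% | 5% (8) | 150/166 = 90.4% | −0.44 |
| 158/174 = 90.8% | 10% (16) | 142/158 = 89.9% | −0.93 |
| 158/174 = 90.8% | 15% (24) | 134/150 = 89.3% | −1.47 |

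The fall runs from 0.44 to 2.01 points, with 8 to 24 evaluated patients discarded. For 155/174 the exact 95% interval is 9.8 points wide; it becomes 10.7 at 10% loss and 11.2 at 15% loss.

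**Does every 12-month failure stay?** No. Under SAP 10.2, a patient with no reliable CSF count at month 12 or later who is a failure at month 18 for any reason is set to failure at month 12. SAP 10.1 counts loss to follow-up at month 18 as failure. Such a patient is an imputed 12-month failure and is also a non-completer, so leaves PP. Let L be the share of all patients lost after month 12 and q the share of those who are imputed failures. The change is (p − L(1 − q))/(1 − L) − p, which is zero when q = 1 − p. For p = 0.87 and L = 5%: q = 0 gives −0.68 points, q = 13% gives 0.00 and q = 20% gives +0.37. For p = 0.91 and L = 5%, zero falls at q = 9%.

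**Against mITT.** In mITT, death and loss by month 12 count as failures (SAP 10.2), and such patients are non-completers who leave PP. Take 155/174 = 89.1% as the mITT rate, with 10% of successes lost later. If 2 of the 19 failures are non-completers of this kind, PP is 139/156 = 89.1%, so there is no shift. If 5 are, PP is 139/153 = 90.8%, above mITT. At 15% loss, 3 are enough: 132/148 = 89.2%.

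**The case against.** The strongest reply is that the text is ambiguous. Protocol 9.3 and SAP 8.2 describe PP by major violations alone, neither document classes loss after month 12 as a major violation, and the sponsor makes that classification at data review. On that reading the patient lost after month 12 could stay. It can also be said that the exemption for inefficacy waives a violation without declaring the patient a completer: a strict reading might remove both groups and a violation-only reading keep both. This stands as evidence of inconsistency. It does not remove the completion requirement from the two sections that define the set, and two programmers could build different 12-month PP sets from these documents.

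A fixed PP set, so that both rates describe the same patients, is a defensible choice. But the documents do not give that reason, and SAP 5 takes the other course for the Evaluable set.

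It is also fair that little depends on this. The SAP makes the 18-month outcome on mITT primary and treats month 12 as intermediate, the analysis is descriptive with no threshold attached, and a time-specific Evaluable analysis sits beside it. That limits the weight of the point.

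A reader might infer that the 12-month PP rate is simply biased downward because only successes can be lost after month 12. The documents do not support this: imputed 12-month failures can leave in the same way, and the sign of the net shift is not fixed. Nor do they support a claim that PP must fall below mITT.

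**Conclusion.** The point holds as a minor defect of definition. Followed as written, the 12-month PP set is selected on events in the six months after the outcome it describes, although the same SAP section avoids this for the Evaluable set.

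The fall of about 0.4 to 2.0 points rests on three conditions: comparison with a PP set anchored at month 12, an assumed 5% to 15% loss of successes, and retention of all failures. It is small beside an exact interval about 10 points wide. If imputed failures make up more than the overall failure share (9% to 13%) of those lost after month 12, the shift reverses. The effect is confined to one descriptive sensitivity analysis; the mITT and 12-month Evaluable results do not change.

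**What to change.** In protocol 9.2 and SAP 5, define PP separately for each time point. Suggested wording: *For the 12-month rate, PP consists of patients followed up to the 12-month visit, or withdrawn before it for inefficacy or intolerance, who had no major violation up to that visit. For the 18-month rate, the same rule applies with the 18-month visit.* Bring protocol 9.3 and SAP 8.2 into line, so that all four places say whether completion is required and whether loss after month 12 excludes a patient.

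The cost is one sentence in each definition, matching edits in the other two sections, and a second PP flag in the analysis dataset. The downside is that the two PP rates will rest on slightly different patients, so each table should state its denominator. If the analysis has already been run, report the result anchored at month 12 alongside it, labelled post hoc.
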